Multiple Interventions During Implant Procedure	No concomitant procedures are to be performed at the time of the WATCHMAN FLX Pro implant procedure with the exception of implantable loop recorder implants/explants. This includes, but is not limited to, cardiac ablation procedures, transcutaneous valve procedures, cardioversions, coronary stent implantation, pacemaker or implantable cardioverter defibrillator generator change, etc.
Statistical Methods	
Analysis Sets	
Analysis sets are listed below.
 
- Intention-To-Treat (ITT): This population includes all subjects who sign an ICF and are enrolled in the study, regardless of whether the study device is implanted.- Implanted: This population includes all subjects who sign an ICF, are enrolled in the study, and are successfully implanted with the study device in the correct position.
Statistical Hypothesis	There is no formal statistical hypothesis for this observational, single-arm study. No statistical inference will be made in the study.
Methods	Outcomes in the overall treatment cohort will be summarized using descriptive statistics for continuous variables (mean, standard deviation, number of observations, minimum and maximum) and discrete variables (percentage and count/sample).

3. Table of Contents

1. TITLE PAGE	1
2. PROTOCOL SYNOPSIS.....	5
3. TABLE OF CONTENTS.....	12
3.1. Table of Figures.....	16
3.2. Table of Tables	16
4. INTRODUCTION	17
4.1. Background.....	17
4.1.1. Atrial Fibrillation, Stroke, and the LAA.....	17
4.1.2. WATCHMAN and LAAO	17
4.1.3. New Features of WATCHMAN FLX Pro.....	18
4.1.4. Cardiac Imaging.....	20
4.2. Study Rationale	20
5. DEVICE DESCRIPTION.....	21
5.1. Device Under Study (Test Device)	21
5.2. Test Device – WATCHMAN FLX Pro LAAC Device Implant and Delivery System	22
5.3. Overview of the WATCHMAN Access System (Access Sheath and Dilator) .	25
6. STUDY OBJECTIVES AND ENDPOINTS	26
6.1. Study Objectives.....	26
6.2. Study Endpoints	26
6.2.1. Primary Endpoint.....	27
6.2.2. Additional Measurements.....	27
7. STUDY DESIGN	28
7.1. Scale and Duration.....	28
7.2. Treatment Assignment.....	29
7.3. Justification for the Study Design.....	29
8. SUBJECT SELECTION.....	30
8.1. Study Population and Eligibility.....	30
8.2. Inclusion Criteria	30

8.3. Exclusion Criteria	30
9. SUBJECT ACCOUNTABILITY.....	31
9.1. Point of Enrollment.....	31
9.2. Withdrawal	32
9.3. Lost to Follow-Up.....	32
9.4. Subject Status and Classification.....	33

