Attempt	
A subject who signs an ICF, meets eligibility criteria, and has had a WATCHMAN Access Sheath inserted to implant the device, but eventually does not receive a WATCHMAN FLX Pro device will be classified as "Attempt." Attempt subjects will be followed for 12 months from the time of the implant attempt and adverse events will be collected. Attempt subjects count towards the enrolment ceiling and will be used for analyses of the endpoints. The original signed ICF must be maintained in the center's study file and the following forms must be completed.
 
• eCRFs in the Baseline and Implant folders• First Follow-up Visit Form(s), except LAA imaging• Adverse Event forms and/or Device Deficiency forms for any reportable adverse event that occurs after signing the ICF• End of Study form for withdrawal 
The date of withdrawal should be indicated in the End of Study form as the point of subject withdrawal.

Implant	
A subject who is successfully implanted with the WATCHMAN FLX Pro device will be classified as "Implant." Successfully implanted subjects are those defined as having device success, where the device has been deployed and implanted in the correct position. These subjects are followed in accordance with the follow-up schedule and data will be included in all study analyses. All applicable case report forms per the protocol must be completed. The original signed ICF and any relevant documentation must be maintained in the center's study file.

Abbreviations: eCRF=electronic case report form; ICF=Informed Consent Form; LAA=left atrial appendage

9.5. *End-of-Study Definition*

This clinical study will be considered completed when subjects are no longer being examined or the last subject's last study visit as outlined in the data collection schedule (**Table 10.1-1** below) has occurred. All enrolled subjects will be evaluated clinically post-implant on the procedure day, at predischarge, at 14 days, 45 days, 3 months, and 12 months post implant procedure (preferably all in-person visits; see **Table 10.1-1** for additional information).

At the point of study completion and/or withdrawal, all open adverse events must be assessed by the investigator. These events must be closed or documented as ongoing. Events assessed as related to the device should be followed through resolution if possible, with the consent of the subject provided for collection of this data.

10. Study Methods

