11.2.1. Analysis Sets

Outcomes in WATCHMAN FLX Pro CT will be assessed on an ITT basis and an implanted basis. The ITT analysis set includes all subjects who sign an ICF (see Section 19) approved by the IEC and who are enrolled in the study (see Section 9.1 for point of enrollment), whether or not the WATCHMAN FLX Pro device is implanted. The implanted analysis set includes ITT subjects who are successfully implanted with the study device in the correct position.

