DEATH	
Cardiovascular Death
 
Any one of the following criteria is met.
 
 • Death due to proximate cardiac cause (e.g., myocardial infarction, cardiac tamponade, worsening heart failure, endocarditis, etc.) • Death caused by noncoronary, non-CNS vascular conditions such as pulmonary embolism, ruptured aortic aneurysm, dissecting aneurysm, or other vascular disease • Death from vascular CNS causes 
 ◦ Hemorrhagic stroke ◦ Ischemic stroke • All-cause mortality during the implant procedure, any procedure-related death within 30 days after the implant procedure or during postoperative hospitalization for the implant procedure (if >30 days), including those related to a complication of the procedure or treatment for a complication of the procedure • Unexplained death (see below) 
Non-cardiovascular Death
 
 • Any death in which the primary cause of death is clearly related to another condition (e.g., trauma, cancer, suicide)

Table 25.2-1: Definitions

Term	Definition
	
Unexplained Death
 
 • Sudden or unwitnessed death defined as a non-traumatic, unexpected fatal event occurring within one hour of the onset of symptoms in an apparently healthy subject. If death is not witnessed, the definition applies when the victim was in good health 24 hours before the event. • Death of unknown causes
DEVICE DEFICIENCY	
Inadequacy of a medical device with respect to its identity, quality, durability, reliability, safety, or performance.
 
Note 1: Device deficiencies include malfunctions, use errors, and inadequate labeling.

DEVICE EMBOLIZATION	Defined as movement of the device during or after deployment such that it dislodges and entirely leaves the LAA or completely loses contact with the LAA.
DEVICE MIGRATION	Defined as shifting of the implant within the LAA to create an inadequate seal where the gap is greater than 5mm at 45 days or later and the physician must intervene (e.g., adjust patient's anticoagulant regimen).
DEVICE RELATED THROMBUS	Thrombus formation on the atrial facing side of the device, possibly resulting in the need for anticoagulation and/or hospitalization.
DEVICE SUCCESS	Defined as implantation of a WATCHMAN FLX Pro device without in-hospital mortality

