Outcomes in WATCHMAN FLX Pro CT will be assessed on an intention-to-treat (ITT) basis and an implanted basis. The ITT analysis set includes all subjects who sign an Informed Consent Form approved by the Independent Ethics Committee (IEC) and are enrolled in the study, whether or not the WATCHMAN FLX Pro device is implanted. The implanted analysis set includes ITT subjects who are successfully implanted with the study device in the correct position.

Endpoints are listed below. Measurements will be collected peri- and post-procedure, predischarge, and at 14 days, 45 days, 3 months and 12 months after the implant procedure, unless specified otherwise.

The primary endpoint is device surface morphology (inclusive of tissue coverage) post implant procedure as assessed over time using the serial advanced imaging modalities of cardiac computed tomography (CT) and transesophageal echocardiography (TEE).

Additional endpoints will include the following:

- Endpoints adjudicated by an Independent Clinical Events Committee (CEC):
 - All-cause mortality (cardiovascular/unknown and non-cardiovascular)
 - Stroke (disabling and non-disabling; ischemic and hemorrhagic)
 - **Note 1:** For subjects diagnosed with a neurological event (e.g., stroke, transient ischemic attack [TIA]), mRS and NIHSS should be performed after the event. It is recommended that the subject be contacted regarding mRS assessment at 90±14

days following any suspected stroke; the simplified mRS questionnaire may be used for this follow-up assessment. It is recommended that imaging be performed after the event to screen for device related thrombus (DRT). If performed, imaging results should be sent to the core laboratory.

- Systemic embolism
- Bleeding: International Society on Thrombosis and Haemostasis (ISTH) major and non-major clinically significant
 - Procedural bleeding (≤ 7 days post-procedure)
 - Non-procedural bleeding (> 7 days post-procedure)
- Pericardial effusion/tamponade requiring pericardiocentesis or surgery
- Endpoints not adjudicated by an Independent Clinical Events Committee (CEC):
- Device success: defined as implantation of a WATCHMAN FLX Pro device without in-hospital mortality
- Assessments by serial imaging modalities (CT and TEE, optional cardiac magnetic resonance imaging [MRI]) at 14 days, 45 days, and 3 months (TEE optional at 3 months if there is no leak at 45 days). Data will be evaluated by an independent core lab.

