7.2. General Statistical Methods

All statistical analyses will be performed using the SAS System software, version 9.2 or later (Copyright[©] 2000 SAS Institute Inc., [name], USA. All rights reserved).

All statistical analyses will be conducted according to applicable Standard Operating Procedures, Work Instructions, and the study-specific statistical analysis plan.

Statistical models that account for censored data will be employed in appropriate circumstances (e.g., for time-to-event outcomes).

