7.2.1. Analysis Sets

Endpoints will be analyzed on an intention-to-treat (ITT) basis and an implanted basis. For ITT analyses, all subjects who sign the IEC-approved study ICF and are enrolled in the study

will be included in the analysis, whether or not a study device was implanted. For implanted analyses, ITT subjects who had the study device implanted in the correct position during the index procedure will be included in the analysis.

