9.3. Rules and Definitions

Binary event rates (proportions) will be calculated on a per subject basis.

The number of subjects included in the outcome rates will be based on subjects who have adequate follow-up (see Section 9.4) and/or have experienced any events.

For baseline categorical variables, “unknown” responses and missing values will not be counted in rate denominators.

The date of last follow-up will be the latest of the following dates for each subject: date of a major event with CEC adjudication, index procedure date, discharge date, and scheduled follow-up visit date.

Days to (event or last known status) = (event or status) date minus procedure date.

Length of hospital stay = discharge date minus procedure date.

In-hospital event rates are calculated as the proportion of subjects who experience the specified event from index procedure through day of discharge out of all subjects enrolled.

Out-of-hospital event rates are calculated as the proportion of subjects who experience the specified event from the day after discharge through the number of days as specified out of all subjects who were discharged following index procedure and have adequate follow-up or have experienced the event as specified.

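### The texts conflict on whether a correctly implanted subject who dies in hospital is in the Implanted set, and the in-hospital denominator, read literally, counts people who had no procedure

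*Protocol*

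**What the plan says.** **Implanted set.** In Protocol 9.4, Table 9.4-1, the Implant class reads: "Successfully implanted subjects are those defined as having device success, where the device has been deployed and implanted in the correct position". Table 25.2-1 gives device success as: "Defined as implantation of a WATCHMAN FLX Pro device without in-hospital mortality". Both synopses, Protocol 6.2.2 and SAP 5.2 give the same definition.

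Protocol 11.2.1 says: "The implanted analysis set includes ITT subjects who are successfully implanted with the study device in the correct position". Both synopses require that subjects "are enrolled in the study, and are successfully implanted with the study device in the correct position", and SAP 5.2 has "ITT subjects who are successfully implanted with the study device in the correct position". SAP 7.2.1, the SAP's own section on analysis sets, drops the word *successfully* and takes "ITT subjects who had the study device implanted in the correct position during the index procedure".

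**In-hospital denominator.** SAP 9.3 computes in-hospital rates from events "from index procedure through day of discharge out of all subjects enrolled". Protocol 9.1 and the note to SAP Figure 6.1-1 treat a subject as enrolled once consent is given. Table 9.4-1 keeps screen failures out of the enrolment ceiling and the primary analyses; the SAP says nothing about them. Protocol 7.1 and SAP 6.1, however, describe the enrolled number as subjects in whom placement is attempted. A general rule in SAP 9.3 rests outcome rates on subjects with adequate follow-up or an event.

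**The concern.** An analysis set whose membership depends on surviving to discharge is selected on an outcome. All-cause mortality and device success are both listed endpoints, and SAP 7.2.1 has endpoints analysed on the ITT and the Implanted basis. If the survival condition applies, Implanted-set mortality at every time point leaves out the in-hospital deaths, and device success in that set cannot be anything but 100%. If the choice between wordings is left open, it may be made after a death is known.

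The denominator issue is of a similar kind. A person who consented but had no procedure cannot have an event between index procedure and discharge. Counting that person adds an event-free subject by definition and lowers each in-hospital rate.

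**Working it through.** The plan gives no figure to reproduce: the study is descriptive and unpowered. The check sets the definitions side by side and then sizes the difference with assumed counts.

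**1. Membership of the Implanted set**

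- Route A: Protocol 11.2.1, both synopses and SAP 5.2 require successful implantation. Table 9.4-1 ties that to device success, and device success requires no in-hospital death. A correctly implanted subject who dies before discharge is out.
- Route B: SAP 7.2.1 requires only correct position at the index procedure. The same subject is in.
- Under route A the subject has no class in Table 9.4-1. The Attempt class is for subjects who did not receive a device, and a screen failure is someone who failed eligibility.

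**2. Size if one such death occurs**

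The protocol maximum is 50. Assume all 50 are correctly implanted, one dies before discharge, no one else dies by the time point considered, and follow-up is complete.

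| Implanted-set quantity | Route A | Route B |
|---|---|---|
| Mortality at a follow-up time point that covers the death | 0/49 = 0% | 1/50 = 2.0% |
| Device success | 49/49 = 100% | 49/50 = 98.0% |

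If 1, 2 or 5 of the 50 were attempts without a device, route B device success is 48/49 = 97.96%, 47/48 = 97.92% or 44/45 = 97.78%. Route A stays at 100%. With no in-hospital death the routes agree.

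**3. Chance that the conflict matters**

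The documents give no in-hospital mortality risk for this device, so the risk p is an assumption. The chance of at least one death among n subjects is 1 − (1 − p)^n.

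| Assumed p | n = 50 (protocol) | n = 25 (SAP) |
|---|---|---|
| 0.1% | 4.9% | 2.5% |
| 0.25% | 11.8% | 6.1% |
| 0.5% | 22.2% | 11.8% |
| 1% | 39.5% | 22.2% |

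**4. In-hospital denominator**

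Let u be the number who consented but had no procedure, on top of 50 attempted. The literal SAP 9.3 rate for x events is x/(50 + u). The documents do not give u.

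| u (assumed) | 3 events | 1 event |
|---|---|---|
| 0 | 3/50 = 6.0% | 1/50 = 2.0% |
| 2 | 3/52 = 5.8% | 1/52 = 1.9% |
| 5 | 3/55 = 5.5% | 1/55 = 1.8% |

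Even at u = 15, one event reads 1/65 = 1.54% rather than 2.0%.

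**The case against.** **On the Implanted set.** Table 9.4-1 classifies subjects and lists forms; it is not where analysis sets are defined. Its sentence carries its own gloss about position, and the follow-up sections repeatedly separate subjects by device position, never by survival. The SAP governs the analyses ("All statistical analyses will be conducted according to applicable Standard Operating Procedures, Work Instructions, and the study-specific statistical analysis plan"), and SAP 7.2.1 keeps the subject. All of this stands and favours retention. It does not close the matter. The SAP itself uses both wordings, nowhere says that in-hospital deaths are retained, and the position-only gloss would give device success a meaning it has nowhere else.

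A reader might go further and infer that the plan excludes in-hospital deaths as a settled rule. The documents do not support that, given the gloss and SAP 7.2.1. Nor do such deaths vanish: they stay in the ITT set, and Protocol 11.2.4 requires all events to be reported for subjects who receive a device. Nor would the in-hospital mortality rate be printed as 0/49, because SAP 9.3 divides in-hospital events by all enrolled, not by the Implanted set. The exposure lies in Implanted-set mortality at the follow-up time points and in device success.

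**On the denominator.** Enrolment is not used in one sense only. Besides the attempt-based wording in Protocol 7.1 and SAP 6.1, Protocol 11.2.2 places eligibility and selection for a device before enrolment. The general SAP 9.3 rule could also remove untreated subjects, because SAP 9.4 counts adequate follow-up in days after the procedure. These points stand: the text is ambiguous rather than plainly wrong. It is also fair that an all-enrolled denominator matches the ITT definition. That cannot serve the implanted basis, though, and a never-attempted subject adds no information to a rate that starts at the procedure.

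One might also read Protocol 11.2.4 or the out-of-hospital rule as contradicting the in-hospital rule. They do not. The former covers event reporting and cut-off days and sets no denominator; the latter must condition on discharge.

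**Conclusion.** The point holds as a minor one, with moderate confidence. One chain of definitions makes Implanted-set membership depend on survival to discharge, while SAP 7.2.1 does not, and nothing in the documents says which prevails for a correctly implanted subject who dies in hospital. With one such death in 50, Implanted-set device success is 100% or 98.0% depending on the wording chosen. With none, nothing changes. The chance of at least one is about 5% to 40% at n = 50, for assumed risks of 0.1% to 1%.

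The literal in-hospital denominator includes people who had no procedure, but other wording points towards attempted subjects. With up to 5 untreated subjects assumed, the shift is at most half a percentage point on a 6% rate.

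The ITT definition needs no change. The study tests no hypothesis, and its imaging primary endpoint is essentially unaffected.

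**What to change.** 1. In Table 9.4-1, remove the link to device success from the Implant class and leave the position condition. A correctly implanted subject who dies in hospital then has a class.
2. Use the SAP 7.2.1 definition in Protocol 11.2.1, both synopses and SAP 5.2, and state that in-hospital deaths remain in the Implanted set.
3. In SAP 9.3, make the in-hospital denominator all subjects with an attempted or completed implant procedure, and Implanted subjects when reporting on the implanted basis.
4. Show screen failures and consented but never-attempted subjects in the disposition table.

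The cost is wording in both documents. The SAP supplied is Revision A, written against protocol Rev C and 25 subjects, while the protocol now allows 50, so it needs revision in any case. SAP 7.3 requires changes to planned analyses to be in an amended SAP approved before the analyses are run. The one downside for the sponsor is that in-hospital rates may look slightly less favourable.

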10.2. Study Candidate Screening

Investigators are responsible for screening all subjects and selecting those who are appropriate for study inclusion as per the clinical IFU. The subjects selected for participation should be from the Investigator's general patient population. Pregnant women and women who plan to become pregnant during the 12 month follow up period are excluded from this study. A woman of childbearing potential must have a negative pregnancy test after signing the consent form and prior to the implant procedure. Women of childbearing potential are required to use highly effective contraceptives during the course of the study (through 12 month follow up visit).

Highly effective contraceptive methods (less than 1% failure rate) include the following:

- Hormonal contraception:
 - birth control pills, ring, or patch that are combined estrogen and progestogen
 - birth control pills, injection, or implant that contains progestogen only
- Intrauterine device (IUD, birth control implant)
- Intrauterine hormone-releasing system (IUS, birth control implant)
- Bilateral tubal occlusion (tubes tied on both sides)
- Vasectomized partner with medical confirmation of success
- True sexual abstinence is acceptable if this is consistent with your preferred, usual, lifestyle. Periodic abstinence is not an acceptable method of contraception.

No study-specified procedures or tests will be done prior to consent, though studies, tests, or procedures performed as part of the normal standard of care may be performed prior to consent.

10.2.1. Strategies for Recruitment and Retention

The WATCHMAN FLX Pro CT Study will include subjects presenting with documented non-valvular atrial fibrillation who are clinically indicated for a WATCHMAN FLX Pro device (see Section 8.2). Because AF prevalence is age-dependent, with a frequency exceeding 15% among individuals 80 years or older², women are well represented in LAAO studies. The inclusion and exclusion criteria are not expected to have a negative effect on recruitment or retention of subjects.

All efforts will be made to minimize attrition (see Section 9.3). Investigators are encouraged to enroll subjects who are willing to comply with the follow-up requirements of the study. If a visit is missed, the center should attempt to contact the subject to reschedule the missed visit and counsel the subject on the importance of maintaining the assigned visit schedule.

10.3. *Subject Informed Consent*

Written informed consent (see Section 19) must be obtained for all qualified subjects who are potential study candidates prior to the subject's implant procedure.

The Investigator/designee who has been trained on the protocol will explain the nature and scope of the study, the potential risks and benefits of participation, and will answer questions for the subject. If the subject agrees to participate, the IEC-approved ICF must be signed and personally dated by the subject or his/her legally authorized representative. The Investigator/designee must sign the ICF prior to subject enrollment. Any additional persons required by the center's IEC to sign the ICF must also comply.

The original, signed document is to be kept with the subject's file and a copy must be provided to the subject. The informed consent process must be documented by the person obtaining consent and the documentation must be placed in the subject's file.

10.4. *Baseline Assessments*

The following assessments must be completed within 30 days prior to the implant procedure, unless otherwise specified below. The study electronic case report forms (eCRFs) identify the specific data points to be collected.

- Confirmation of eligibility criteria and contraindications per the clinical IFU
- Clinical assessments
 - Demographics, including age at time of consent and sex
 - Medical and cardiac history; includes cardiovascular diseases, AF type (paroxysmal, persistent, permanent), prior history of stroke/transient ischemic attack (TIA), previous cardiac procedures, history of bleeding and location, eligibility for oral anticoagulation, indication for LAA occlusion
 - Physical assessment
 - Risk factor assessments, including HAS-BLED and CHA2DS2-VASc scores⁴¹
 - Current antiplatelet, anticoagulation, and other cardiovascular medications
 - mRS score and NIHSS score

Note 1: Neurological status as determined by the mRS score should also be determined following any suspected stroke; it is recommended that the subject be contacted regarding an mRS assessment at 90 ± 14 days post-stroke; the simplified mRS questionnaire³⁸ may be used for this follow-up assessment and may be collected by telephone.

- Approximately 15 mL of blood will be drawn for analysis which will include baseline serum creatinine (may be obtained up to 30 days prior to consent) and biochemical markers including measures of coagulation, platelet and endothelial activation and inflammation. The following is the list of blood analyses performed:
 - Platelet count
 - Mean platelet volume
 - Immature platelet fraction
 - Plasma selectin
 - INR
 - Activated partial thromboplastin time
 - Von Willebrand factor
 - D-dimer
 - Prothrombin Fragment 1+2
 - Hgb
 - Brain natriuretic peptide
 - C-reactive protein
 - Creatinine
 - eGFR
- Imaging assessments
 - Either CT or TEE assessment of the LAA must be carried out within 14 days prior to the implant procedure to confirm LAA size and to document that eligibility criteria have been met. Results must be sent to the core lab. This preprocedural imaging assesses appendage anatomy and device sizing and excludes the presence of a LAA thrombus. Suitability for attempted device implantation will be assessed as follows.
 - Using multiple imaging planes, LAA size/shape, number of lobes in the LAA, and location of lobes to ostium will be determined.
 - Absence of thrombus will be confirmed. If an intracardiac thrombus is visualized, device implantation will not be attempted. Re-assessment may be scheduled per the physician's discretion.
 - Measurements of the LAA ostium width and LAA depth will be recorded. The measured maximum LAA ostium width must be ≥ 14.0 mm and ≤ 36 mm to accommodate the available WATCHMAN FLX Pro device sizes.
 - Cardiac MRI assessment (including 4D cardiac MRI flow analysis of the LA and LAA) is optional but if performed, the results must be sent to the core lab.
 - All protocol required pre-procedural imaging will be performed by trained individuals and in accordance with core lab instructions (see Section 12.3). Copies of the imaging results will be sent to the core lab for independent analysis. Additionally, copies of all LAA imaging will be saved to disk at the center and available to the sponsor upon request. The center and subject identification number should be clearly identified on the disks.

10.5. *Pre-procedure Medications*

Pre-procedure medications are listed below and should be recorded on the eCRFs.

- Single antiplatelet therapy (aspirin or P2Y₁₂ inhibitor) is recommended prior to device implantation. A loading dose should be administered the day before the implant procedure. Dosing should be per standard of care. The choice of loading dose medication is at the discretion of the treating physician but should be the same as the intended post-procedure antiplatelet therapy.
- Patients that are actively treated by SAPT pre-procedure should not receive a loading dose
- Anticoagulant therapy (e.g., unfractionated heparin) must be administered per local standard of care during the implant procedure, with a recommended target activated clotting time (ACT) of ≥ 250 seconds during the implantation procedure.
- Prophylactic antibiotic therapy should be given according to local practice. The choice of antibiotic drug is left to the investigator's discretion.

10.6. *Implant Procedure*

The preparation of the subject for the transcatheter procedure will be performed following standard techniques. Refer to the WATCHMAN FLX Pro LAA Closure Device clinical IFU and the WATCHMAN[®] Access System or the WATCHMAN[™] TruSeal[™] Access System IFU for detailed instructions regarding device use.

The following information will be collected in the eCRF during the procedure. Additional data to be collected may be outlined in the eCRF.

- Date of procedure
- WATCHMAN FLX Pro LAA Closure Device size used
- Commercially available WATCHMAN Access System or the WATCHMAN[™] TruSeal[™] Access System used
- Procedural ICE data with results sent to the core laboratory
- Medications
- Adverse event assessment (see Section 18)

10.7. *Predischarge*

The subject may be discharged from the hospital when clinically stable, at the Investigator's discretion per local standard of care. Prior to discharge from the hospital, a complete safety event assessment must be done. The study eCRFs identify the specific data points to be collected. This includes evaluation of any procedure-related adverse event (AE), serious adverse event (SAE), adverse device effect (ADE), serious adverse device effect (SADE),

unanticipated serious adverse device effect (USADE), and any device deficiency with associated treatment.

Note 1: For subjects diagnosed with a neurological event (e.g., stroke, TIA), mRS and NIHSS should be performed after the event. It is recommended that the subject be contacted regarding an mRS assessment at 90 ± 14 days post-neurological event; the simplified mRS questionnaire³⁸ may be used for this follow-up assessment and may be collected by telephone. It is recommended that imaging be performed after the event to screen for DRT. If performed, imaging results should be sent to the core laboratory.

Antiplatelet therapy post implant procedure is recommended to reduce the risk of thrombotic or thromboembolic complications if there are no contraindications to these medications. Subjects must be treated with single antiplatelet therapy (SAPT; aspirin or P2Y₁₂ inhibitor) for at least 3 months following WATCHMAN FLX Pro implantation. Extended therapy may be administered per physician choice.

Prior to discharge, clinical staff should review the study follow-up visit schedule with the subject to maximize follow-up compliance.

10.8. *Follow-up*

All subjects successfully implanted with a WATCHMAN FLX Pro device will be evaluated at 14 days, 45 days, 3 months, and 12 months post implant procedure. Subjects who are enrolled but not implanted with a WATCHMAN FLX Pro device in the correct position will be followed for safety through 12 months after the initial attempted implant procedure by telephone or review of clinical files but will not undergo imaging assessments or evaluation of biochemical markers including measures of coagulation, platelet and endothelial activation and inflammation.

In the event that study personnel learn of a subject's hospitalization outside the study center, the center should make every effort to obtain copies of reports or results based on tests (e.g., echocardiogram) and/or procedures performed on the study subject.

10.8.1. *14-Day Follow-up (14 Days ± 3 Days)*

All enrolled subjects will be evaluated 14 days after the implant procedure. The study eCRFs identify the specific data points to be collected as listed below.

- Complete safety event assessment, including any SAE, ADE, SADE, USADE, device deficiency with associated treatment, and any CEC event regardless of seriousness and device relationship.

Note 1: For subjects diagnosed with a neurological event (e.g., stroke, TIA), mRS and NIHSS should be performed after the event. It is recommended that the subject be contacted regarding an mRS assessment at 90 ± 14 days following any suspected stroke; the simplified mRS questionnaire³⁸ may be used for this follow-up assessment and may be collected by telephone. It is also recommended that imaging be performed to screen for DRT. If performed, imaging results should be sent to the core laboratory.

- All antiplatelet medications, which should be administered in accordance with local standard of care. Subjects must be treated with SAPT (aspirin or P2Y₁₂ inhibitor) for at least 3 months following WATCHMAN FLX Pro implantation.
 - Approximately 15 mL of blood will be drawn for analysis of biochemical markers measures of coagulation, platelet and endothelial activation and inflammation. The following is the list of blood analyses performed:
 - Platelet count
 - Mean platelet volume
 - Immature platelet fraction
 - Plasma selectin
 - INR
 - Activated partial thromboplastin time
 - Von Willebrand factor
 - D-dimer
 - Prothrombin Fragment 1+2
 - Hgb
 - Brain natriuretic peptide
 - C-reactive protein
 - Creatinine
 - eGFR
- TEE is required for all subjects who have a WATCHMAN FLX™ Pro LAA Closure Device implanted in the correct position and should be performed per the core lab guidelines, including assessment of device seal and device surface morphology (inclusive of tissue coverage) post implant procedure. Results must be sent to the core lab for independent analysis.
- CT is required for all subjects who have a WATCHMAN FLX™ Pro LAA Closure Device implanted in the correct position and should be performed per the core lab guidelines, including assessment of device seal, device-related thrombus (including hypoattenuated thickening [HAT]) and device surface morphology (inclusive of tissue coverage) post implant procedure. Results must be sent to the core lab for independent analysis.
- Cardiac MRI assessment, including 4D cardiac MRI flow analysis of the LA and LAA, is optional but if performed, the results must be sent to the core lab for independent analysis.

Subjects who are enrolled but do not receive a WATCHMAN FLX Pro Device in the correct position during the implant procedure will be followed for safety through 12 months after the initial attempted implant procedure by telephone or review of clinical files but will not undergo imaging assessments or evaluation of biochemical markers including measures of coagulation, platelet and endothelial activation and inflammation.

10.8.2. 45-Day Follow-up (45±15 Days) and 3-Month Follow-up (90±30 Days)

All enrolled subjects will be evaluated 45 days and 3 months after the implant procedure. The study eCRFs identify the specific data points to be collected as listed below.

- Complete safety event assessment, including any SAE, ADE, SADE, USADE, device deficiency with associated treatment, and any CEC event regardless of seriousness and device relationship.
- **Note 1:** For subjects diagnosed with a neurological event (e.g., stroke, TIA), mRS and NIHSS should be performed after the event. It is recommended that the subject be contacted regarding an mRS assessment at 90±14 days following any suspected stroke; the simplified mRS questionnaire³⁸ may be used for this follow-up assessment and may be collected by telephone. It is also recommended that imaging be performed after the event to screen for DRT. If performed, imaging results should be sent to the core laboratory.
- All antiplatelet medications, which should be administered in accordance with local standard of care. Subjects must be treated with SAPT (aspirin or P2Y₁₂ inhibitor) for at least 3 months following WATCHMAN FLX Pro implantation.
- Physical assessment as per local standard of care
 - Approximately 15 mL of blood will be drawn for analysis of biochemical markers which will include measures of coagulation, platelet and endothelial activation and inflammation. The following is the list of blood analyses performed:
 - Platelet count
 - Mean platelet volume
 - Immature platelet fraction
 - Plasma selectin
 - INR
 - Activated partial thromboplastin time
 - Von Willebrand factor
 - D-dimer
 - Prothrombin Fragment 1+2
 - Hgb
 - Brain natriuretic peptide
 - C-reactive protein
 - Creatinine
 - eGFR
- TEE is required for all subjects who have a WATCHMAN FLX™ Pro LAA Closure Device implanted in the correct position at 45 days and should be performed per the core lab guidelines, including assessment of device seal and device surface morphology (inclusive of tissue coverage) post implant procedure. Results must be sent to the core lab for independent analysis.

- TEE is optional at 3 months for subjects who have a WATCHMAN FLX Pro LAA Closure Device implanted in the correct position if there is no leak at 45 days. However, if TEE is performed, results must be sent to the core lab for independent analysis.
- CT is required for all subjects who have a WATCHMAN FLX Pro LAA Closure Device implanted in the correct position and should be performed per the core lab guidelines, including assessment of device seal, device-related thrombus (including HAT) and device surface morphology (inclusive of tissue coverage) post implant procedure. Results must be sent to the core lab for independent analysis.
- Cardiac MRI assessment, including 4D cardiac MRI flow analysis of the LA and LAA, is optional but if performed, the results must be sent to the core lab for independent analysis.

Subjects who are enrolled but not implanted with a WATCHMAN FLX Pro Device in the correct position during the implant procedure will be followed for safety through 12 months after the initial attempted implant procedure by telephone or review of clinical files but will not undergo imaging assessments or evaluation of biochemical markers including measures of coagulation, platelet and endothelial activation and inflammation.

10.8.3. 12-Months Follow-up (365±30 Days)

All subjects successfully implanted with a WATCHMAN FLX Pro Device will be evaluated at 12 months after the implant procedure. The study eCRFs identify the specific data points to be collected as listed below.

- Complete safety event assessment, including any SAE, ADE, SADE, USADE, device deficiency with associated treatment, and any CEC event regardless of seriousness and device relationship.

Note 1: For subjects diagnosed with a neurological event (e.g., stroke, TIA), mRS and NIHSS should be performed after the event. It is recommended that the subject be contacted regarding an mRS assessment at 90 ± 14 days following any suspected stroke; the simplified mRS questionnaire³⁸ may be used for this follow-up assessment and may be collected by telephone. It is also recommended that imaging be performed after the event to screen for DRT. If performed, imaging results should be sent to the core laboratory.

- All antiplatelet and other cardiovascular medications should be administered in accordance with local standard of care.

